7. STUDY POPULATION AND RECRUITMENT

Describe who and how many subjects will be invited to participate. Include age, gender and other pertinent information.

Normotensive and postmenopausal women and women with high BP (ages 50-70 years) will be recruited. A total of 60 women will be recruited (30 normotensive and 30 high BP). Subjects will be recruited from campus and local community- posting flyers and advertisement in local newspapers, in physicians' offices, community centers or events, through professional societies, or online (UD classifieds, website). In addition, we will conduct blood pressure screenings in the community.

Attach all recruitment fliers, letters, or other recruitment materials to be used. If verbal recruitment will be used, please attach a script.

Recruitment flyers are attached.

Describe what exclusionary criteria, if any will be applied.

Women will be excluded from the study if they have a history of any heart disease, kidney or liver disease, history of blood clots, pulmonary embolism, deep vein thrombosis, stroke, cancer, diabetes, or any other chronic disease. Women will also be excluded from the study if they use tobacco products (including cigarettes and chewing tobacco), are using hormone therapy, are pregnant, or if their body mass index is greater than 35. Women will be excluded if resting blood pressure is greater than 180/100 mmHg, or less than 100/60 mmHg at the initial screening.

Describe what (if any) conditions will result in PI termination of subject participation.

We are assessing serum electrolytes, creatinine and blood pressure at baseline and after 1 week of losartan administration. If serum electrolytes (potassium >5.2 mmol/L), creatinine levels (>50% over baseline values) rise too high, or blood pressure (less than 100/60 mmHg) drops too low, the study physician [name] will be contacted to determine if the subject will be instructed to stop taking the medication and will be excluded from the study.

8. RISKS AND BENEFITS

List all potential physical, psychological, social, financial or legal risks to subjects (risks listed here should be included on the consent form).

There are no known risks associated with obtaining height, weight, resting electrocardiogram, and resting blood pressure. The 24-hour blood pressure monitor may interrupt sleep in some participants.

Microdialysis: Subjects will probably experience some pain and bruising like that from a blood draw. However, we will use ice to numb the skin during insertion of the fibers. Also, the small needle size (23 gauge) reduces pain during placement of the fibers. Subjects will probably not have pain after the fiber is in place but may feel a little pain when the fiber is removed from the skin. Similar to a blood draw subjects may become lightheaded or faint. Mild pressure with sterile gauze would be applied to stop any slight bleeding that may occur. Infection is possible. Sterile techniques and supplies are used to minimize risk. We will apply a sterile bandage after the experiment.

Substances infused through microdialysis fibers: The amount of substance that enters the skin is very small. However, there is a chance of having an adverse reaction to the substances. This reaction could produce redness, itching, rash, and/or swelling. Although unlikely, it is possible that a more serious reaction could also cause fever, breathing problems, changes in heart rate, convulsions, and/or collapse. If a serious reaction should occur, emergency medical help will be summoned right away.

Lactated Ringer's solution: This fluid contains salt, potassium, lactate, and chloride. The acid content is similar to the body's fluids. A bad reaction to this fluid is highly unlikely.

BQ-123, BQ-788, and SNP: Only minute amounts of these substances enter the nickel-sized area of skin around the tubing. [name] has previously used BQ-123, BQ-788, and SNP infusions in the skin without adverse reactions^{1,2}. Additionally, these drugs have been used in the skin by other researchers without adverse reactions³.

Laser Doppler: Lasers can damage the eye if pointed into the eye for a prolonged period of time. We will not turn the laser on until it is taped to the skin surface and will turn it off before removing it.

Local Heating: We measure the temperature of the skin under the holders. The skin will feel very warm but will not hurt. The heating will make the skin under the holders red similar to taking a hot bath. The redness will not last more than several hours. Some people may be more sensitive to the heating than others. If a subject's arm feels too hot, we will reduce or stop the heating.

Losartan: Losartan is a drug commonly used to treat high blood pressure. Common side effects may include cold or flu symptoms (stuffy/runny nose, sneezing, sore throat, fever), dry cough, muscle cramps, pain in the legs or back, stomach pain, nausea, or diarrhea, headache, hypotension, dizziness or light-headed, hyperkalemia, tired feeling, trouble concentrating, or sleep problems (insomnia). Other side effects may include pain or burning when urinating, wheezing or chest pain, rapid heart rate, increased thirst, loss of appetite, swelling, weight gain, urinating less than usual or not at all, confusion, or mood changes. Women will be given a list of potential side effects with instructions to either call 911 (severe allergic reaction) or call the study investigators.

Exercise Test: The risks of performing an exercise test are low. As summarized in the American College of Sports Medicine Guidelines for Exercise Testing and Prescription (10th ED, 2018)⁴, there are ~6 cardiac events per 10,000 tests. All participants (normotensives and hypertensives) are initially screened by the NMPCC to ensure they are otherwise healthy and not high risk (i.e., no known disease, no signs or symptoms of disease). The study physician, [name], will determine whether hypertensive participants are able to complete the exercise test based on their blood pressure and screening results since hypertension is a CVD risk factor.

In your opinion, are risks listed above minimal* or more than minimal? If more than minimal, please justify why risks are reasonable in relation to anticipated direct or future benefits.

(*Minimal risk means the probability and magnitude of harm or discomfort anticipated in the research are not greater than those ordinarily encountered in daily life or during the performance of routine physical or psychological examinations or tests)

More than minimal, however the risks associated with the study are low. Data collected from this study will help to understand the mechanisms contributing to hypertension in women.

What steps will be taken to minimize risks?

The risk of infection during blood draws, endothelial cell collection, and microdialysis fiber placement is minimized by using sterile materials and technique throughout the protocol. Subject discomfort due to microdialysis fiber placement is minimized by the application of ice to the area for 10 minutes prior to fiber insertion. Losartan is a drug commonly used to treat patients with high blood pressure. Using losartan may cause an electrolyte imbalance, and rarely kidney failure. Women will be instructed not to drink alcohol while taking losartan, and also to avoid potassium supplements or salt substitutes, and NSAIDs. We will assess electrolytes and creatinine levels in all women taking losartan on day 7 of administration. If serum potassium is >5.2 mmol/L or creatinine is >50% over baseline, the study physician will be contacted to advise the participant to discontinue the study medication and determine whether they should discontinue the study. The study physician will determine if additional medical follow-up is needed (ER, PCP). Women will keep in close contact with study investigators. A list of potential side effects of using losartan will be given to women, with instructions to either call 911 (if signs of an allergic reaction occur such as hives, difficulty breathing, swelling of the face, lips, tongue, or throat), or to call the study investigators. The participant will be given contact information to reach the study investigator and Nurse Managed Primary Care Center if questions or concerns arise during the study protocol. The study investigator can reach [name], who can then call the participant if needed.

A clinical exercise physiologist and nurse practitioner will directly supervise the exercise test, and follow set guidelines published by the American College of Sports Medicine for stopping the test. The NMPCC will send the test results to be read and interpreted by their cardiologist, [name]. In the event of a positive test or if additional follow up is needed, the NMPCC will contact the participant's primary care doctor.

Describe any potential direct benefits to participants.

There may be no direct benefit to subjects for participating in this research study however they will be provided the results of screening blood work and VO₂max test when they complete the study. The results will be interpreted and provided to the participants PCP if additional follow-up is needed.

Describe any potential future benefits to this class of participants, others, or society.
This study may provide new information regarding the mechanisms contributing to hypertension in women.

If there is a Data Monitoring Committee (DMC) in place for this project, please describe when and how often it meets.

N/A

9. COMPENSATION

Will participants be compensated for participation?

Yes

If so, please include details.

Women with high BP: Subjects completing all aspects of the study will receive \$275.00. If a participant is excluded due to elevated blood levels (visit 3), they will receive \$100.00. Participants that do not complete visit 5 (exercise test) will receive \$225.00. They will receive the compensation at the end of the study in the form of a check.

Normotensive women – hormone intervention: Subjects completing all aspects of the study will receive \$200.00. They will receive the compensation at the end of the study in the form of a check. Participants that do not complete visit 4 (exercise test) will receive \$150.00.

10. DATA

Will subjects be anonymous to the researcher?

Information obtained from this study will be kept strictly confidential. Participants are not anonymous to the researcher, and will not be individually identified except by a participant number known only to the investigators.

If subjects are identifiable, will their identities be kept confidential? (If yes, please specify how)

Informed consents and medical history questionnaires will be kept in a separate locked filing cabinet from any data with participant numbers. A list of names and participant numbers will be encrypted and kept on a password protected computer. The list will be kept for 5 years after study completion; the list will be deleted and digital media scrubbed. Information obtained in the medical history form is used only by the Nurse Managed Health Center at the University of Delaware, and electronic records are stored in a secure HIPAA compliant database.

How will data be stored and kept secure (specify data storage plans for both paper and electronic files. For guidance see <http://www.udel.edu/research/preparing/datasorage.html>)

Information obtained from this study will be kept strictly confidential. Subjects will not be individually identified, except by subject number, known only to the investigators. All data stored as paper files or digitally will be kept indefinitely. The paper files are stored in a locked cabinet. A list of names and participant numbers will be kept on a password-protected computer. All data will be stored in a locked cabinet or password protected computer indefinitely. All data will be encrypted. The data will be stored and archived for potential use in other, future studies. Information obtained in the medical history form is used only by the Nurse Managed Health Center at the University of Delaware, and electronic records are stored in a secure HIPAA compliant database. In the event of any publication or presentation resulting from the research, no personally identifiable information will be revealed.

How long will data be stored?

All data will be stored in a locked cabinet or password protected computer indefinitely. All data will be encrypted.

Will data be destroyed? YES NO (if yes, please specify how the data will be destroyed)

Will the data be shared with anyone outside of the research team? YES NO (if yes, please list the person(s), organization(s) and/or institution(s) and specify plans for secure data transfer)

How will data be analyzed and reported?

Cutaneous vascular conductance (CVC) will be calculated as mean SkBF/mean arterial pressure. While the results of this research will be published, neither participant name nor identity will be revealed.

11. CONFIDENTIALITY

Will participants be audiotaped, photographed or videotaped during this study?

No

How will subject identity be protected?

Information obtained from this study will be kept strictly confidential. Subjects will not be individually identified, except by subject number, known only to the investigators. All data stored as paper files or digitally will be kept indefinitely. The paper files are stored in a locked cabinet. While the results of the research may be published, subjects' names and identities will not be revealed.

Is there a Certificate of Confidentiality in place for this project? (If so, please provide a copy).

No

Sample size estimates were calculated for our main outcome variables in Specific Aim 1 based on previously published data in normotensive and pre-hypertensive adults utilizing arterial infusions of the ET-1 receptor antagonist. A three level 2x2 General Linear Mixed Model will be used to compare normotensive and hypertensive PMW on the outcomes. The hierarchical structure is needed as sites are nested within measurements, which are nested within individuals. The model assumptions of linearity and normality, will be evaluated using Box-Cox and Shapiro-Wilk tests, respectively. Outliers and influential cases will be screened for and removed. The covariance structure will be chosen using nested model comparisons. Violations of the assumptions will be remedied using transformations suggested by the Box-Cox test. *Post-hoc* comparisons will have the Bonferroni adjustment applied. The alpha is set at 0.05 for each analysis, and will be adjusted by the number of primary dependent variables to control for multiple comparisons. In order to find a large effect ($\rho\eta^2 = 0.50$), a sample of size of 38 women is required to achieve a power greater than 0.8. In order to account for screen failures, subject attrition and potential microdialysis fiber failure, we will recruit 60 women (30 normotensive and 30 hypertensive).

A Mixed Design ANOVA will be used to evaluate if losartan administration alters endothelial ET-1 protein expression ETB receptor expression on endothelial cells, along with ETA and ETB receptor expression on vascular smooth muscle cells in hypertensive PMW compared to that of normotensive PMW. Since values are expressed as ratios, if the assumptions of the Mixed Design ANOVA are not satisfied a Generalized Linear Mixed Model will be used. In order to find a moderately small effect ($\rho\eta^2 = .09$), a sample of size of 38 is required to achieve a power greater than 0.8. The model also assumes of linearity, sphericity, and normality, which will be evaluated using Box-Cox, Mauchly's, and Shapiro-Wilk tests, respectively. Outliers and influential cases will be screened for and removed. *Post-hoc* comparisons will have the Bonferroni adjustment applied. The alpha is set at 0.05 for each analysis, and will be adjusted by the number of primary dependent variables to control for multiple comparisons. Although we are planning on matching our groups based on age, body composition, VO_2max , and time since menopause, these may be potential covariates will be compared between groups using t-tests for continuous data and tests for χ^2 tests for categorical data. If a covariate is significantly different between groups it will be included in the analysis.

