Hypertension is major health problem for postmenopausal women. Hypertension is more likely to be uncontrolled in women, despite medication use. Medications to block the angiotensin II pathway are commonly used to treat hypertension. However, recent data in animals suggest that multiple pathways are involved in blood pressure control in females. Specifically, blocking the angiotensin II pathway along with the endothelin-1 pathway resulted in a larger drop in blood pressure in these animals compared to single drug therapy. These blood pressure lowering effects observed in the female animals may be related to the interactions between angiotensin II and endothelin-1. Both angiotensin II and endothelin-1 are potent vasoconstrictors that can cause an increase in blood pressure, and these substances interact to cause additive effects on constricting blood vessels. The aims of this study are to examine how angiotensin II and endothelin-1 interact to regulate blood vessel function in hypertensive postmenopausal women. To do this, we will recruit women with elevated blood pressure not taking blood pressure medications, and test their blood vessel function on 2 separate visits: 1) baseline, and 2) after 14-days of losartan (an angiotensin II receptor blocker). Blood vessel function will be assessed using a technique called microdialysis, which involves placing tiny sterile plastic tubes (microdialysis probes) in the surface layer of the skin on the forearm, and blood flow will be measured using a small disk with a laser. We will also recruit normotensive women to complete 2 visits to assess blood vessel function pre/post 14 days as a control (no losartan administration).

6. PROCEDURES Describe all procedures involving human subjects for this protocol. Include copies of all surveys and research measures.

We will recruit postmenopausal women with high BP (≥ 130 and/or 80 mmHg) and normotensive postmenopausal women (ages 50-70 years). Women with high BP will complete 5 visits (screening/orientation, VO₂max test, Blood Vessel Assessment 1, Blood draw to check electrolytes and kidney function, and Blood Vessel Assessment 2), and normotensive women will complete 4 visits (screening/orientation, VO₂max test, Blood Vessel Assessment 1, and Blood Vessel Assessment 2).

Procedures in Women with high BP (5 visits):

Visit 1: Screening/orientation: The first visit is about 1 hour long and includes

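### For microdialysis skin blood flow, the stated 2x2 model leaves its factors unnamed and, whichever are meant, cannot hold the losartan-by-antagonist term that the aim needs

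*Combined protocol and SAP*

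**What the plan says.** The project summary that precedes Section 6 gives the aim: to "examine how angiotensin II and endothelin-1 interact to regulate blood vessel function in hypertensive postmenopausal women". It adds: "Blood vessel function will be assessed using a technique called microdialysis". High-BP women are tested at baseline and after 14 days of losartan. Normotensive women are tested twice, 14 days apart, without losartan, as the control.

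Section 6 (ET-1 receptor antagonists) perfuses four fibers: Ringers, BQ-123 (ET-A), BQ-788 (ET-B), and both. Flow is measured at 33°C and again with heating to 42°C. In both groups the second vessel assessment is described as identical to the first.

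The analysis text that could apply to these data is:

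- Statistical Plan, first paragraph: "A three level 2x2 General Linear Mixed Model will be used to compare normotensive and hypertensive PMW on the outcomes". The reason given for the hierarchy is that "sites are nested within measurements, which are nested within individuals". Also: "The covariance structure will be chosen using nested model comparisons". Alpha is 0.05 and "will be adjusted by the number of primary dependent variables to control for multiple comparisons".
- Statistical Plan, second paragraph: a mixed-design ANOVA to "evaluate if losartan administration alters endothelial ET-1 protein expression" and receptor expression. It does not cover skin blood flow.
- Section 10, on how data will be analyzed: "Cutaneous vascular conductance (CVC) will be calculated as mean SkBF/mean arterial pressure", with no model.

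**The concern.** The design has three crossed factors: group (2), visit (2) and antagonist condition (4). Whether losartan changes the response to endothelin-receptor blockade is a visit x antagonist question. With the normotensive women as time control it becomes group x visit x antagonist. A 2x2 holds two factors, so a 2x2 that compares the groups has room for only one of the other two.

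Two things are at stake. First, a significant result from the 2x2 as written could arise with no change in the antagonist response. Second, because the factors and the contrast are unnamed, the contrast could be chosen after the data are seen. The point concerns microdialysis conductance only; the brachial and pressure-waveform measures have no antagonist condition.

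**Working it through.** **The plan's own figure.** The first paragraph requires 38 women for partial eta-squared 0.50 at power above 0.8, without saying which term this belongs to. With f² = 0.50/(1 − 0.50) = 1, a between-group F test at alpha 0.05 (non-centrality f²N) has power 0.79 with 10 women, 0.88 with 12 and about 1.00 with 38. So 38 is not reproduced. That is a separate matter, but it means the figure gives no assurance about the losartan-by-antagonist term.

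**What each possible 2x2 contains.**

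| Factors | Visit x antagonist | Group x visit x antagonist |
|---|---|---|
| group x visit (sites pooled) | no | no |
| group x two-level antagonist (visits pooled) | no | no |
| ET-A x ET-B (visits and groups pooled) | no | no |

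**What the estimates mean (no SD needed).** Let a shift be the change over visits in high-BP women minus that in normotensive women. Sites are ordered Ringers, ET-A, ET-B, both.

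1. Sites pooled: the estimate is the mean of the four site shifts.
   - ET-A-specific: (0 + 1 + 0 + 1)/4 = 0.50.
   - Uniform, no antagonist interaction: (0.5 + 0.5 + 0.5 + 0.5)/4 = 0.50.
2. Visits pooled: the group x ET-A estimate is b + L/2. Here b is the baseline group difference in the ET-A response and L is the losartan shift in that response.
   - b = 0, L = 1: 0 + 0.50 = 0.50.
   - b = 0.5, L = 0: 0.5 + 0 = 0.50.
   - A baseline group difference in overall flow cancels and contributes 0.

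Only group x visit x ET-A returns L itself.

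**Illustrative rejection rates.** Assumptions, none given in the documents: SDs woman 1, visit 0.5, site 1; 19 women per group; two-sided alpha 0.05/2 = 0.025, taking the two thermal phases as the two primary variables; 36 df.

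- Sites pooled: SE = √(4(0.5² + 1/4)/19) = 0.324, so 0.5/0.324 = 1.54 and the rate is 0.23. It is 0.45 for visit SD 0 and 0.10 for visit SD 1. Simulation gave 22% and 23% in the two cases.
- Visits pooled: SE = √((1 + 2s²)/19), where s is the between-woman SD of the ET-A response. For s = 0, SE = 0.229 and the rate is 0.45 in both cases. For s = 0.5 or 1, SE = 0.281 or 0.397 and the rate is 0.30 or 0.15.
- Group x visit x ET-A: SE = √(4/19) = 0.459, so 1/0.459 = 2.18 and the rate is 0.45 when L = 1. Simulation gave about 2.5% in both cases with no losartan-by-ET-A effect.

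**Power of candidate contrasts** for a shift of one site SD at both ET-A-blocked sites (non-central t). Here τ is the visit-to-visit SD of the ET-A response, n is women per group and N = 2n. Alpha is 0.025.

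| Contrast | SE | df | 38 women | 60 women |
|---|---|---|---|---|
| Group x visit x ET-A, τ = 0 | √(4/n) | 6(N − 2) | 0.47 | 0.69 |
| same, τ = 0.5 | √(5/n) | N − 2 | 0.36 | 0.56 |
| same, τ = 1 | √(8/n) | N − 2 | 0.23 | 0.36 |
| BQ-123 minus Ringers, group x visit | √(8/n) | 6(N − 2) | 0.24 | 0.38 |
| Visit x ET-A, high-BP women only, τ = 0 | √(2/n) | 6(n − 1) | 0.79 | 0.95 |
| same, τ = 0.5 | √(2.5/n) | n − 1 | 0.63 | 0.86 |

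At alpha 0.05 the first row is 0.58 and 0.78. If only the BQ-123-alone site shifts by 1, the factorial ET-A effect is 1/2. Its power is then 0.12 (38) or 0.19 (60), against 0.24 or 0.38 for BQ-123 minus Ringers.

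**Why the covariance matters.** If τ is omitted from the model, the residual mean square averages (3 + τ²)/3 while the ET-A contrast needs 1 + τ². For τ = 1 the ratio is 2/1.33 = 1.5, and for τ = 0.5 it is 1.25/1.083 = 1.15. In simulation (19 per group) the type I error at nominal 0.05 was 0.048, 0.067 and 0.107 for τ = 0, 0.5 and 1.

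**The case against.** The strongest reply is that the plan is silent rather than wrong. The sentence on nesting justifies random levels; it does not list fixed effects. The label 2x2 may describe group x visit, with antagonist condition understood as a further within-visit factor. Planned Bonferroni post-hoc comparisons fit a four-level site factor better than two two-level factors. Further, the sample size is tied to Specific Aim 1, whose wording is not in the documents. If that aim is only the comparison of the two groups, the model may suit it.

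Part of this stands. A reader might infer that the plan deliberately treats drug site as nothing more than a nested level. The text does not say so; that is an inference from where sites are mentioned. A reader might also infer that any baseline difference between groups would mimic a losartan effect when visits are pooled. It would not: only a difference in the ET-A response does.

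The rest does not remove the point. Unspecified post-hoc comparisons do not supply an interaction absent from the stated model. Running the 2x2 site by site is not stated either, and significance at one site but not at another is not a test of interaction. If Specific Aim 1 concerns only the group comparison, then the losartan effect on conductance has no stated analysis at all.

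**Conclusion.** The concern holds in this form: as stated, no analysis of microdialysis conductance contains the losartan-by-antagonist term that the aim in the project summary needs, whichever factors the 2x2 has. This rests on reading that aim as whether losartan alters the response to receptor blockade.

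The paired 0.50 results follow from the contrasts alone. The rejection rates and powers are illustrations under assumed SDs, shifts and two primary variables. In particular, the 45% with visits pooled assumes that the ET-A response does not vary between women.

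It would be too strong to say that the trial cannot answer its question. All four conditions are measured at both visits in both groups, so the data will support the right model. For that reason this is something that should be fixed in the analysis text, not a flaw in the design.

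**What to change.** For conductance in each thermal phase, replace the 2x2 with fixed effects group x visit x antagonist (four sites, or ET-A no/yes x ET-B no/yes) and all interactions. Keep woman and visit-within-woman as random levels. Add variation in antagonist response, between women and between visits, to the candidates in the planned covariance comparison.

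Before the data are seen:

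- Name the primary losartan-by-antagonist contrast: group x visit x antagonist, or visit x antagonist within hypertensive women.
- Say whether each antagonist is tested as a factorial effect or as a single site minus Ringers.
- State how many primary dependent variables divide alpha, and declare any further split across contrasts as an addition.
- State the power for the chosen contrast beside the existing sample-size sentence.

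A group x visit model on each site-minus-Ringers response also addresses the aim. It is a different test with different power, so the plan should choose between them.

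No new procedures are needed; each phase has 2 x 2 x 4 = 16 fixed-effect parameters instead of 4. The drawback is modest power for the three-way contrast. At alpha 0.025 the smallest shift with 80% power is 1.42 site SD with 38 women or 1.13 with 60, rising to 1.64 or 1.29 if τ = 0.5. The contrast within hypertensive women is more powerful but gives up the time control.
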